4.2.1.1 Study Procedure Modifications in Response to the COVID-19 Pandemic

The modifications listed below are designed to enable safety monitoring of subjects enrolled in the trial through an extended blood sampling window as well as to maintain trial integrity for the primary and secondary endpoints by enrolling all remaining patients in Cohort B (to obtain both the CMR and CTA as well as extended dosing data), which has had a greater dropout rate further impacted by COVID-19.

- 1 If the Visit 6 (Day 70-84) follow-up visit cannot be conducted in person due to the coronavirus disease (COVID-19) pandemic, the following study procedure modifications are permissible:
 - (a) Where possible, a subject should return to the clinic as soon as possible after the planned Visit 6 (Day 70-84) visit but no more than 150 days post dose 1 for blood sample collection (except for future use samples), including immunogenicity, PK, and PD, as listed in the Schedule of Study Procedures ([Table 8](#) and [Table 9](#)) for Day 70-84.
 - (b) However, assessment of AEs/SAEs and concomitant medications should be done via telephone contact within the originally specified window for Visit 6 (ie, Day 70-84).
 - (c) If a subject returns to the clinic for blood sample collection within the extended window, any AEs/SAEs that occur between the telephone contact and the date of this visit should also be recorded.

The modifications in study procedures listed above (1a-c) are only permitted due to COVID-19-related constraints impacting the subject, site, or health system; otherwise, the study procedures should be conducted within the timeframes originally specified in the Schedule of Study Procedures ([Table 8](#) and [Table 9](#)).

- 2 All subjects will be randomized into Cohort B [REDACTED] Regimen). Subjects will be randomized in a 1:1 ratio to receive MEDI6012 or placebo. This modification will remain in place until the end of the study.

Table 8 Treatment Period and Follow-up Procedures: Cohort A (Red Regimen)

Study Period	Treatment Period										Follow-up	
Visit Number	V1 (Inpatient)							V2	V3	V4	V5	V6
Procedure / Study Day	Day 1					Anytime between Days 1-3	Day 3 (48 ± 8 hours)	Day 10 (±1 day) Phone	Day 17 (± 1 day)	Day 24 (± 1 day) Phone	Day 31 (± 1 day)	Days 70-84 ^a
	Screening	Pre-PCI										
Written or verbal informed consent	X											
Verify eligibility criteria	X											
Screening ECG (clinical) ^b	X											
Abbreviated medical history review	X											

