4.6 Treatment Assignment and Blinding

4.6.1 Methods for Assigning Treatment Groups

An IXRS will be used for randomization to a treatment regimen. A subject is considered randomized into the study when the investigator notifies the IXRS that the subject meets eligibility criteria. Subjects will be randomized in a 1:1 ratio to one of 2 cohorts, Cohort A (██████████) and Cohort B (██████████). Within each dose regimen, subjects will be randomized in a 2:1 ratio to receive MEDI6012 or placebo:

Cohort A

- MEDI6012, ████████ (n ~ 180)
- Placebo, ████████ (n ~ 90)

Cohort B

- MEDI6012, ████████ (n ~ 180)
- Placebo, ████████ (n ~ 90)

In the event that a dose regimen is dropped at the interim analysis, subjects will be randomized in a 1:1 ratio to receive MEDI6012 or placebo for the remaining dose regimen.

Infarct location will be controlled during the randomization process, ensuring a similar distribution of anterior vs. non-anterior infarcts between the active and placebo groups. In addition, the distribution of subjects with anterior versus non-anterior MIs will be monitored over the course of the study. The goal is that > 50% of the final randomized population will be anterior MI. Therefore, the number with non-anterior MI will be monitored via the IXRS and capped by the study team.

Investigational product (MEDI6012 or placebo) must be administered as soon as possible before pPCI (preferably > 10 minutes prior) and no later than 4 hours from the time investigational product is reconstituted. If there is a delay in the administration of

investigational product such that it will not be administered within the specified timeframe, the study monitor must be notified immediately.

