4.8.2 Sample Size

A total of 90 subjects per arm will provide 80% power to detect a [REDACTED] reduction in infarct size between MEDI6012 [REDACTED] group and combined placebo group ([REDACTED] placebo groups), and between MEDI6012 [REDACTED] group and combined placebo group with one-sided alpha 0.05 assuming a coefficient of variation of [REDACTED]. A total of 180 subjects per arm is

required as a █% rate of exclusion from the primary efficacy analysis population is expected due to █ in the infarct-related artery on initial angiography and other reasons for subsequent exclusion or drop-out (Botker et al, 2010; Hausenloy et al, 2013). A █ reduction in infarct size is thought to be clinically significant, assuming it would equate to an approximate █% absolute reduction in infarct size in a future trial that enrolls subjects with large infarcts. A █% absolute reduction in infarct size is associated with a █% relative risk reduction in heart failure and mortality. With this same sample size, the power to detect a █% absolute difference in EF between each MEDI6012 group and combined placebo group with █ alpha █ is > █% assuming standard deviation █%. For the secondary endpoint of non-calcified coronary plaque regression/progression, there will be > █% power to detect a █ mm³ change in NCPV from index CTA to the 10-12 week CTA between MEDI6012 group and placebo group with █ assuming a common standard deviation of █ mm³ and █% drop-out. It is estimated that the study will involve approximately 43 sites in approximately 10 countries.

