2.3 Treatment Assignment and Blinding

An IXRS will be used for randomization to a treatment regimen. A subject will be considered randomized into the study when the investigator notifies the IXRS that the subject meets eligibility criteria. Randomization will be stratified by infarct location. Subjects will be randomized in a 1:1 ratio to one of 2 cohorts, Cohort A ([REDACTED]) and Cohort B ([REDACTED]). Within each dose regimen, subjects will be randomized in a 2:1 ratio to receive MEDI6012 or placebo, see Figure 2.1.

[figure not shown]
In the event that a dose regimen is dropped at the interim analysis, subjects will be randomized in a 1:1 ratio to receive MEDI6012 or placebo for the remaining dose regimen.

The randomization will be stratified by infarct location, ensuring a similar distribution of anterior vs non-anterior infarcts between the active and placebo groups. In addition, the distribution of subjects with anterior versus non-anterior MIs will be monitored over the course of the study. The goal is that > 50% of the final randomized population will be anterior MI. Therefore, the number with non-anterior MI will be monitored via the IXRS and capped by the study team.

This is a blinded study in which MEDI6012 and placebo are nearly identical in appearance. The subject/legal representative and the Sponsor will not be aware of the treatment received

(ICH E9). The unblinded individual preparing the first dose of investigational product for administration in the catheterization laboratory will be aware of the treatment received. The unblinded administrator will be trained to not reveal treatment assignment to the investigator or other clinical and study staff. The site will be asked to take reasonable steps to maintain the blind. Subsequent doses after Dose 1 will be prepared by an unblinded pharmacist. Sites are encouraged to take all reasonable steps to keep site staff involved in follow up assessments after Day 1 blinded to randomization group.

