3.4.1.3 Primary Efficacy Analysis

The primary efficacy endpoint is the infarct size in 10-12 weeks post MI. The endpoint will be log-transformed due to its skewed distribution and be analyzed by means of 2-sample t-test. The treatment effect is estimated by the geometric mean ratio of MEDI6012 to placebo as well as its 95% CI. Infarct size records with zero value, will be imputed by half of the minimum of the non-zero records prior to the log transformation.

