3.4.2.3 Secondary Efficacy Analyses

EF, myocardial mass, and left ventricular volumes will be analyzed using t-test, if appropriate, based on the Primary Efficacy Analysis Population, the Efficacy Analysis Population – TIMI 2-3; Efficacy Analysis Population – TIMI 0-3; as treated, and the ITT Population.

Change from index CTA in NCPV will be analyzed using t-test, if appropriate, based on CTA Analysis, As-treated, and ITT Populations.

Parameters will first be evaluated for normality which will be evaluated using Q-Q plots.

If the distribution appears to be normal, the endpoint will be analyzed by a 2-sample t-test. The treatment effect is estimated by difference in means of MEDI6012 to placebo as well as its 95% CI.

If the distribution appears to be log-normal, the endpoint will be log-transformed due to its skewed distribution and be analyzed by a 2-sample t-test. The treatment effect is estimated by the geometric mean ratio of MEDI6012 to placebo as well as its 95% CI.

Non-parametric (distribution-free) methods will be applied to the endpoint data if applicable.

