4 INTERIM ANALYSIS

Two interim analyses are planned. The objectives of the first interim analysis will be to assess futility and potentially to drop a dose regimen. The analysis, which will be conducted after 30% of the Primary Efficacy Analysis Population (assumed 40% rate of exclusion from the primary efficacy analysis population is expected due to TFG 2 or 3 flow in the infarct-related artery on initial angiography and other reasons for subsequent exclusion or drop-out) based on the original sample size ($N = 74$) is enrolled, will require that $> 50\%$ of subjects ($N > 37$) have acute anterior STEMI and have completed their final study visit. The first interim analysis will be conducted through the Independent Data Monitoring Committee (IDMC). The second interim analysis is planned to accelerate decision on future development options for MEDI6012 and will be performed once 60% of the Primary Efficacy Analysis Population (assumed 50% rate of exclusion from the primary efficacy analysis population is expected due to TFG 2 or 3 flow in the infarct-related artery on initial angiography and other reasons for subsequent exclusion or drop-out) based on the revised sample size ($N = 162$) is enrolled and will require that $> 50\%$ of subjects ($N > 81$) have acute anterior STEMI and have completed their final study visit. Details of the second interim analyses will be specified in the unblinding plan. The sponsor and Principal Investigator will monitor the statistical assumptions in a blinded fashion and schedule the interim analyses accordingly.

The assessment of futility will be based on predictive power, which is conditional power averaged over the distribution of the observed treatment effect at the time of interim analysis. The futility analysis will include all available data at the time of the interim data cut.

The predictive power based on the empirical trend observed at the interim analysis will be calculated by

$$\text{predictive power } pp = \Phi\left(\frac{z_\tau - z_{1-\alpha/2}\sqrt{\tau}}{\sqrt{1-\tau}}\right)$$

τ is the information fraction at the interim analysis, z_τ is the observed value of the test statistic at the interim, α is the two-sided significance level at the final analysis based on the original protocol, and Φ is the standardized normal density function.

Each MEDI6012 dose regimen will be compared to the combined placebo group (pooled over dose regimens).

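### After Amendment 6 only Cohort B recruits, at 1:1, so Cohort A active is compared with a partly later placebo group and the SAP's t-tests have no period term

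*Protocol*

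**What the plan says.** **Allocation before Amendment 6.** Protocol 4.6.1 randomises 1:1 to Cohort A or B, and then: "Within each dose regimen, subjects will be randomized in a 2:1 ratio to receive MEDI6012 or placebo".

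**Allocation from Amendment 6 (04May2020).** Protocol 4.2.1.1 puts all further subjects in Cohort B for the rest of the study: "Subjects will be randomized in a 1:1 ratio to receive MEDI6012 or placebo. This modification will remain in place". One reason given is that Cohort B is the cohort "which has had a greater dropout rate further impacted by COVID-19".

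**Comparator.** Protocol 4.8.2 sizes the trial for each MEDI6012 group against placebo combined over cohorts, at one-sided alpha 0.05. SAP 4, on the interim, says: "Each MEDI6012 dose regimen will be compared to the combined placebo group (pooled over dose regimens". For the final analysis, SAP 3.4.1.3 speaks only of the ratio of MEDI6012 to placebo.

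**Analysis.** For infarct size (SAP 3.4.1.3): "The endpoint will be log-transformed due to its skewed distribution and be analyzed by means of 2-sample t-test". For the secondary endpoints (SAP 3.4.2.3): "If the distribution appears to be normal, the endpoint will be analyzed by a 2-sample t-test". Neither section has a period term, a stratum or a concurrent-control rule.

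**What SAP v3.0 (03Dec2020) took from Amendment 6.** It adopts the two possible database locks and adds a COVID-19 section (3.9), where the analyses are optional and unspecified. Its description of allocation is unchanged: "Within each dose regimen, subjects will be randomized in a 2:1 ratio to receive MEDI6012 or placebo, see Figure 2.1". The only 1:1 provision in SAP 2.2 and 2.3 applies when a regimen is dropped at the interim.

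**The concern.** Randomisation protects a plain two-sample comparison only while the allocation ratio stays constant, or when the change is modelled. For Cohort A neither holds: its active arm stops recruiting while its placebo comparator continues. If late subjects have larger infarcts, Cohort A looks better than it is; if smaller, a real benefit is hidden. Cohort A is one of the two regimens the trial was sized to test, and the trial is meant to guide later development, so either error matters. The documents do not say whether infarct size changed, but the switch came during the pandemic, when the evaluable population could plausibly change.

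**Working it through.** **Plan's own figures.** Active: 540 × 1/2 × 2/3 = 180 per regimen. Combined placebo: 2 × 540 × 1/2 × 1/3 = 180. With 50% exclusion (SAP 4) this leaves 90 per arm. All agree with Protocol 4.8.2. The interim counts also reproduce: 0.30 × 414 × 0.60 = 74.5 (stated 74) and 0.60 × 540 × 0.50 = 162.

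**Assumed inputs.**
- N1, the number randomised before Amendment 6 took effect: 400 to 500.
- R, the late/early ratio of infarct size: 1/1.2 to 1.2.
- Evaluable fraction: 50% throughout.
- SD of log infarct size: 0.65 to 1.0. The lower value comes from SAP 4, where 50% predictive power matches an 18% reduction. That gives a final SE of -ln(0.82)/1.96 = 0.101. With 414 × 0.60/3 = 82.8 per arm, SD = 0.101/√(2/82.8) = 0.65. As a check, 20% predictive power then falls at a 6.6% reduction (SAP: about 7%). This predates the Amendment 5 re-sizing; 1.0 is an upper value.

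**Formulas**, with N2 = 540 - N1:
- Evaluable Cohort A active = 0.5 × N1/3
- Evaluable combined placebo = 0.5 × (N1/3 + N2/2); Cohort B active is the same
- Late share of placebo w = (N2/2)/(N1/3 + N2/2); Cohort A active 0
- Bias on the log scale = w × ln R
- SE = SD × √(1/n_A + 1/n_P)
- Type I error = 1 - Φ(1.645 - bias/SE)

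**Worked case, N1 = 400, R = 1.2, SD = 0.652.** n_A = 66.7 and n_P = 101.7. w = 70/203.3 = 0.344. Bias = 0.344 × 0.182 = 0.0628. SE = 0.652 × 0.1576 = 0.103. Type I error = 1 - Φ(1.645 - 0.611) = 15.1%. With SD 1.0 it is 10.6%.

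**Cohort A one-sided type I error (nominal 5%), over SD 0.65 to 1.0:**

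| R | N1 = 400 (w = 34%) | N1 = 500 (w = 11%) |
|---|---|---|
| 1.05 | 6.2-6.9% | 5.4-5.6% |
| 1.1 | 7.5-9.2% | 5.7-6.2% |
| 1.2 | 10.6-15.1% | 6.5-7.4% |
| 1/1.1 | 2.5-3.2% | 4.0-4.3% |
| 1/1.2 | 1.2-2.1% | 3.3-3.8% |

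At N1 = 450, w = 23%.

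**Power when late infarcts are smaller.** 80% power at 90 versus 90 implies an effect of 2.486 × √(2/90) = 0.371 SD. At N1 = 400, Cohort A power is Φ(0.371/0.1576 - 1.645) = 76.0% without drift. With R = 1/1.2 it is 54-62%.

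**Simulation** (40,000 runs, N1 = 400, R = 1.2, SD 0.652): rejection under the null was 14.9% for the Cohort A t-test, 5.0% with a period factor, 5.0% against concurrent placebo, and 4.7% for Cohort B versus combined placebo.

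**Other contrasts at N1 = 400.**
- Pooled A+B versus placebo: 34% of placebo and 70/(266.7 + 70) = 21% of active is late. Type I error is 7.4-9.0% at R = 1.2.
- NCPV (Cohort B only, 2:1 then 1:1): 70/(66.7 + 70) = 51% of placebo and 34% of active is late. An assumed 0.2-SD drift in the 10-12 week change gives 7.0-7.6% with 30-50% evaluable, or 3.2-3.5% in the other direction.

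**The case against.** **The Cohort A final contrast is inferred.** True: SAP 3.4.1.3 does not name the placebo group, and redacted or unshown parts of the SAP could hold more. But both places that do name a comparator for each regimen name combined placebo, and the pooled alternative is also unbalanced over time. The ambiguity is itself a reason to state the comparator.

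**The large figures need a large drift.** Also true. ln 1.2 = 0.182 is close to -ln 0.82 = 0.198, the 18% reduction that SAP 4 calls minimally detectable. No passage reports drift in infarct size. The smaller drifts, R = 1.05 to 1.1, are the fairer guide.

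**The dropout remark is weak evidence.** It was written at Amendment 6, so it describes subjects already randomised, not a difference between the two periods. It shows only that the pandemic was affecting evaluability.

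**Evaluability may differ by cohort.** At an assumed 60% (A) and 40% (B) with N1 = 400, the late placebo share falls to 29.6% and the worst case from 15.1% to 13.6%. The Cohort B contrast is then balanced only as randomised: 34.4% of evaluable Cohort B active is late against 29.6% of placebo. A period factor handles this too.

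**SAP 3.9 could cover it.** Its wording is permissive and names no model, so it prespecifies nothing.

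**Conclusion.** The concern holds and should be fixed. The allocation change follows directly from the protocol, and SAP v3.0 does not account for it. Cohort A active versus combined placebo is open to bias of w × ln R on the log scale, where w is about 11% to 34% for N1 = 500 to 400. Over that range, Cohort A's nominal 5% type I error becomes 5.4-6.9% for a 5% rise in infarct size, 5.7-9.2% for 10% and 6.5-15.1% for 20%. Falls of the same ratios make the test conservative and cost power. These are sensitivity ranges: N1, R and the CV are not in the documents, and no drift has been shown. Cohort B versus combined placebo on the CMR endpoints is not affected as randomised. NCPV and a pooled A+B contrast are affected less.

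**What to change.** - In SAP 3.4.1.3 and 3.4.2.3, replace the t-tests with a linear model (log scale for infarct size) with arm (Cohort A active, Cohort B active, placebo) and period as factors. Define period by the randomisation scheme in force when the subject was randomised. Two levels are enough, because allocation is constant within each scheme, provided the Cohort B effect does not differ by period.
- Add the same factor to the Cohort B-only NCPV analysis.
- Report Cohort A against concurrently randomised placebo as a sensitivity analysis.
- State which placebo subjects each regimen is compared with in the final analysis.
- Update SAP 2.2 and 2.3 to the allocation used since Amendment 6.

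This should be settled before unblinding; a period term added afterwards would be post hoc. No new data are needed.

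Cohort A power, at the effect the trial was sized for:

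| N1 | t-test | Period model | Concurrent placebo only |
|---|---|---|---|
| 500 | 79.2% | 78.2% | 77.3% |
| 400 | 76.0% | 72.4% | 69.0% |
| 300 | 70.1% | 63.7% | 58.3% |

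Cohort B loses no power under the period model. The larger loss from concurrent placebo alone is why it is proposed only as a sensitivity analysis.

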4.3 Description of Study Procedures

There are times where the protocol requires more than one procedure to be completed at the same time point. Whenever vital signs, 12-lead ECGs, and blood draws are scheduled for the same nominal time, the assessments should occur in the following order: 12-lead ECG, vital signs, and then blood draws (with the exception of Visit 1 [Day 1], where the order of vital signs and then blood draws may not be possible due to the acute nature of this visit and as the subject may have invasive blood pressure measurements). The timing of the first two assessments should be such that it allows the blood draw (eg, PK blood sample) to occur at the exact nominal time.

4.3.1 Medical History and Physical Examination, Weight, and Vital Signs

A brief and targeted medical history screening will be performed focusing on inclusion/exclusion criteria.

A full physical examination will be conducted anytime between Day 1 and 3 prior to administration of [REDACTED] and at the final study visit (Day 70-84).

Physical examinations will be performed by a physician or a qualified designee with examination of the following body systems: respiratory; CV; gastrointestinal; musculoskeletal; focused neurologic (to the extent of determining whether or not the subject is willing and able to cooperate with the required study procedures in the investigator's judgment); dermatologic; hematologic/lymphatic. When a targeted physical exam is required, evaluation of selective body systems will be at the judgement of the physician or qualified designee based on subject presentation.

Any focal deficit identified at baseline should be documented in the electronic case report form (eCRF). Clinically significant abnormal findings will be recorded at baseline and follow-up.

Weight will be measured immediately following PCI once feasible with regards to equipment availability and appropriateness for the patient's clinical status. Height can be measured anytime between Days 1 and 3 and weight repeated on the days specified in the Schedules of Procedures.

Vital sign measurements (blood pressure [BP], respiratory rate, heart rate, and body temperature) will be measured at the time points specified in the Schedules of Procedures. Invasive blood pressure measurements may be recorded when intra-arterial monitoring is available. When non-invasive blood pressures are taken, the subject should be supine and the subject's arm must be at the same height (at the level of their heart) during each BP measurement.

Subjects should refrain from smoking or drinking caffeinated beverages within 4 hours prior to vital signs measurements.

4.3.2 ECG

ECGs will be conducted at the time points presented in the Schedules of Procedures.

The investigator may add extra 12-lead ECG safety assessments if there are any abnormal findings or if the investigator considers it is required for any other safety reason. Scheduled ECGs and any ECGs done for safety purposes should be scanned for digital storage.

4.3.3 Systemic/Local Tolerability

Site staff will check the injection site(s) for local reactions and assess for systemic reactions at the times specified in the Schedules of Procedures. Local and systemic reactions will be recorded as AEs according to the criteria described in Section 5.4.

4.3.4 Clinical Laboratory Tests

A Laboratory Manual will be provided to the sites that specifies the procedures for collection, processing, storage, and shipment of samples, as well as laboratory contact information, specific to this clinical research study.

Clinical laboratory safety will be performed in a central clinical laboratory, unless specified as “local labs” in the schedule of procedures. Abnormal laboratory results should be followed up at the principal investigator’s discretion.

The following clinical laboratory tests will be performed:

Serum Chemistry

- Calcium
- Chloride
- Potassium
- Sodium
- Bicarbonate
- AST
- ALT
- Alkaline phosphatase (ALP)
- Total bilirubin
- Gamma glutamyl transferase
- Creatinine
- Glucose
- Albumin
- Blood urea nitrogen

Note for serum chemistries: Tests for AST, ALT, ALP, and total bilirubin must be conducted concurrently and assessed concurrently.

Hematology

- White blood cell count with automated differential (by central laboratory)
- Red blood cell count
- Hematocrit
- Hemoglobin
- Platelet count
- Mean corpuscular volume
- Mean corpuscular hemoglobin concentration

Other Laboratory Tests

- Cystatin C
- Glutamate Dehydrogenase
- Creatine Kinase (CK)
- Troponin
- NT-proBNP
- Luteinizing Hormone ^a

- Follicle Stimulating Hormone ^a

^a Female subjects only.

[figure not shown]
